6.2. Laboratory Procedures/Evaluations**6.2.1. Clinical Laboratory Evaluations**

For all subjects, a CBC, chemistry, and urinalysis will be conducted at the Baseline and Day 85 Visits. If an abnormal laboratory assessment is returned from the Baseline assessments, consideration will be given by the investigator as to the continued participation of the subject in the study. Details are provided in the Laboratory Manual. Blood samples will be taken per standard venipuncture techniques. The following will be assessed:

CBC: White blood cell (WBC) count (with automated differential for absolute neutrophils, lymphocytes, monocytes, eosinophils, and basophils), red blood cell (RBC) count, haemoglobin, hematocrit, mean corpuscular volume (MCV), mean corpuscular haemoglobin (MCH), mean corpuscular haemoglobin concentration (MCHC), and platelet count;

Chemistry: Glucose, albumin, total protein, calcium, sodium, potassium, chloride, CO₂ (bicarbonate), blood urea nitrogen (BUN), creatinine, alkaline phosphatase, alanine amino transferase (ALT), aspartate amine transferase (AST), and total bilirubin;

Urinalysis: Color, clarity, specific gravity, pH, protein, glucose, and leukocyte esterase. If the results are abnormal or further analysis is requested by the site, the sample will undergo microscopic analysis for red blood cells, white blood cells, and squamous epithelial cells.

For all WOCBP, a UPT will be conducted at the Screening Visit, Baseline Visit (if >7 days from Screening Visit), and the Day 29, 57, and 85 Visits. The assessment will be done using a test kit with a minimum sensitivity of 25 mIU/mL. Details for collecting and testing urine for the UPT are provided in the Laboratory Manual.

6.2.2. Specimen Preparation, Handling, and Storage

Specimen preparation, handling, shipment, and storage for the CBC, chemistry and urinalysis are described in the Laboratory Manual.

6.3. Study Schedule

6.3.1. Screening Visit

At the Screening Visit (Day -28 to Day 1), the following will be conducted:

- Obtain written informed consent/assent
- Conduct medical history and review of systems
- Obtain subject's demographics
- Obtain subject's height and weight
- Conduct UPT (WOCBP only)
- Collect urine sample for UDS
- Perform IGA
- Calculate BSA of total AD involvement
- Identify a target lesion (selected photography sites only)
- Review eligibility criteria
- Query subject for concomitant medications

If the subject is found to be eligible for participation in the study, the Baseline Visit procedures may then be conducted. If the subject requires any washout period, this period must be completed prior to the Baseline Visit. Subjects found to be ineligible will be screen failed and the reason for screen failure will be recorded. Subjects that do not meet eligibility requirements (e.g. require washout from prohibited medications or have an active infection) may be re-screened once they meet eligibility requirements (e.g. washed out from the prohibited medication(s) or cleared an active infection).

6.3.2. Baseline Visit

If the subject is deemed eligible and proceeds to enrollment on the same day, in addition to the screening assessments the following will be conducted:

- Collect blood sample for CBC and chemistry
- Collect urine sample for urinalysis
- Assess Signs of AD prior to application of study drug
- Collect EASI score prior to application of study drug
- Collect I-NRS prior to application of study drug
- Randomize subject to study drug treatment
- Apply study drug on subject's AD lesions (see Section 5.1.5)
- Monitor subject for AEs 15 minutes after application of study drug
- Photographs and Signs of AD scoring of target lesion (selected sites only)
- Train subject in proper application of study drug
- Weigh and dispense study drug
- Dispense study diary (Day 1 through Day 28) and train the subject in entering administration times and daily pruritus score.

If the subject is not enrolled on the same day as the Screening Visit, the following will be conducted at the Baseline Visit:

- Review eligibility criteria
- Review medical history and review of systems
- Query subject for adverse events since the signing of the informed consent/assent and changes in concomitant medications
- Collect blood sample for CBC and chemistry
- Collect urine sample for urinalysis
- Conduct UPT (WOCBP only)
- Collect urine sample for UDS
- Perform IGA prior to application of study drug
- Calculate BSA of total AD involvement
- Assess Signs of AD score prior to application of study drug
- Collect EASI score prior to application of study drug
- Collect I-NRS prior to application of study drug
- Photographs and Signs of AD scoring of target lesion (selected sites only)
- Randomize subject to study drug treatment
- Apply study drug on subject's AD lesions (see Section 5.1.5)
- Monitor subject for AEs 15 minutes after application of study drug
- Train subject in proper application of study drug
- Weigh and dispense study drug

- Dispense study diary (Day 1 through Day 28) and train the subject in entering administration times and daily pruritus score.

6.3.3. Study Drug Application Period

At the Day 1 Visit, the subject will receive their first study drug application at the clinical site during the Baseline Visit. Subjects will be trained in the correct application of the study drug and provided an ample supply of study drug to complete BID dosing through Day 28. The first application of study drug will occur in the morning and the second application approximately 8 to 12 hours later. A diary will be maintained documenting compliance with application of the self-administered application and daily pruritus score. At the Day 29 Visit, the subject will be provided an ample supply of study drug to complete dosing through Day 56. At the Day 57 Visit, the subject will be provided an ample supply of study drug to complete dosing through Day 84. The final application of study drug will be applied by the subject on the evening of Day 84 or, if the Day 85 Visit is delayed, the evening prior to the Day 85 Visit.

6.3.4. Day 15 Visit

The Day 15 Visit is conducted to ensure the continuing safety of the subject and to monitor compliance with the BID application of study drug. Subjects will be instructed to not apply their morning application of study drug until they are seen in the clinic. If the clinic visit is in the afternoon, the subject should apply their regular morning application and apply the evening application in the clinic, as long as the dose is at least 6 hours after the morning dose. At the Day 15 Visit (Day 15 ± 3 days) the following will be conducted.

- Query subject for any AEs which have occurred since the last visit
- Query subject for changes in concomitant medications
- Perform IGA prior to application of study drug
- Calculate BSA of total AD involvement
- Assess Signs of AD score prior to application of study drug
- Collect EASI score prior to application of study drug
- Collect I-NRS prior to application of study drug
- Photographs and Signs of AD scoring of target lesion (selected sites)
- Have subject apply study drug on their AD lesions (see Section 5.1.5)
- Review study diary and confirm compliance with study drug applications
- Confirm compliance with study drug applications by weighing pumps

6.3.5. Day 29 Visit

Subjects will be instructed to not apply their morning application of study drug until they are seen in the clinic for the Day 29 Visit. If the clinic visit is in the afternoon, the subject should apply their regular morning application and apply the evening application in the clinic, as long as the

dose is at least 6 hours after the morning dose. At the Day 29 Visit (Day 29 \pm 3 days) the following will be conducted.

- Query subject for any AEs which have occurred since the last visit
- Query subject for changes in concomitant medications
- Conduct UPT (WOCBP only)
- Perform IGA prior to application of study drug
- Calculate BSA of total AD involvement
- Assess Signs of AD prior to application of study drug
- Collect EASI score prior to application of study drug
- Collect I-NRS prior to application of study drug
- Photographs and Signs of AD scoring of target lesion (selected sites only)
- Have subject apply study drug on their AD lesions (see Section 5.1.5)
- Collect study drug and study diary and confirm compliance with study drug applications by weighing returned pumps
- Dispense study diary (Day 29 through Day 56)
- Weigh and dispense study drug.

6.3.6. Day 57 Visit

Subjects will be instructed to not apply their morning application of study drug until they are seen in the clinic for the Day 57 Visit. If the clinic visit is in the afternoon, the subject should apply their regular morning application and apply the evening application in the clinic, as long as the dose is at least 6 hours after the morning dose. At the Day 57 Visit (Day 57 \pm 5 days) the following will be conducted:

- Query subject for any AEs which have occurred since the last visit
- Query subject for changes in concomitant medications
- Conduct UPT (WOCBP only)
- Perform IGA prior to application of study drug
- Calculate BSA of total AD involvement
- Assess Signs of AD score prior to application of study drug
- Collect EASI score
- Collect I-NRS
- Photographs and Signs of AD scoring of target lesion (selected sites only)
- Have subject apply study drug on their AD lesions (see Section 5.1.5)
- Collect study drug and study diary and confirm compliance with study drug applications by weighing returned pumps
- Dispense study diary (Day 57 through Day 84)
- Weigh and dispense study drug.

6.3.7. Day 85 Visit/End of Study Visit

The final application of study drug will occur on the evening prior to the Day 85 Visit. If the Day 85 visit is delayed, the subject should continue BID application until the evening before the Day 85 Visit. At the Day 85 Visit (Day 85 \pm 5 days), the following will be conducted:

- Collect and weigh returned study drug pumps
- Collect study diary
- Query subject for adverse events that occurred since the previous visit
- Query subject for changes in concomitant medications
- Collect blood sample for CBC and chemistry
- Collect urine sample for urinalysis
- Conduct UPT (WOCBP only)
- Perform IGA
- Calculate BSA of total AD involvement
- Assess Signs of AD score
- Collect EASI score
- Collect I-NRS
- Photographs and Signs of AD scoring of target lesion (selected sites only)
- Discharge subject from study

6.3.8. Early Termination Visit

If a subject terminates the study early for reasons other than an AE, attempts will be made to complete the assessments required for the Day 85 Visit.

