	
The final study drug application will be applied in the evening prior to the Day 85 Visit.
 
Subjects will return to the clinic for their final visit on Day 85 for safety assessments; blood samples for CBC and chemistry, and urine samples for urinalysis. A UPT will be conducted for WOCBP. Subjects will be queried for adverse events and changes in concomitant medications since their previous visit. Returned study drug will be weighed and diaries will be reviewed for compliance. The site will obtain IGA, BSA of AD, Signs of AD score, and EASI Score. Subjects will be asked to rate their pruritus using the I-NRS. At selected sites, the target lesion will be photographed and scored with the Signs of AD score.
 
If a subject discontinues from the study early, all Day 85 assessments will be completed.
 
After completion of study assessments, the subject will be discharged from the study.

Statistical Methods
	
All statistical processing will be performed using SAS[®] unless otherwise stated.
 
Analysis Sets:
 
This study will be evaluated using 3 analysis sets: intent-to-treat (ITT), per protocol (PP), and safety. Efficacy conclusions will be drawn from the ITT analysis set. The ITT analysis set will consist of all randomized subjects with at least one post-baseline efficacy assessment and will be based on randomized study group, regardless of study drug received. The PP analysis set will be used to support the efficacy findings in the ITT analyses and will include subjects with no major protocol deviations. Safety conclusions will be drawn from the safety analysis set. The safety analysis set will include all subjects that received at least one application of study drug and had at least one post-baseline safety assessment with treatment based on study drug received regardless of randomization group.
 
Demographics will be summarized using the safety analysis set by baseline age, gender, race, ethnicity, height, weight, and BMI. The primary efficacy analysis will be conducted on the ITT population. For continuous variables, the mean, standard deviation (SD), median, and range will be presented along with the 95% confidence interval (CI).

Categorical variables will be summarized by proportions along with the 95% CI.

Handling of Missing Data:

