3.2. Study Endpoints

The primary endpoint for the study is the proportion of subjects with an Investigator's Global Assessment (IGA) success defined as an IGA score of "Clear" (0) or "Almost Clear" (1) with at least a 2-grade improvement from Baseline at Day 85.

The secondary endpoints for the study are:

- The proportion of subjects with an EASI 75 score at Day 85,
- The proportion of subjects with an EASI 50 score at Day 85,
- The change from Baseline in the Signs of AD score at Day 85,
- The proportion of subjects with an IGA of Clear or Almost Clear at Day 85,
- The proportion of subjects with at least a 2-grade improvement in ISGA from Baseline at Day 85,
- The change from Baseline in the percent of body surface area (BSA) affected by AD at Day 85,
- The time to achieve IGA success, and
- The change from Baseline to Day 85 in the Itch-Numerical Rating Scale (I-NRS)

Exploratory analyses will be conducted for:

- The change from Baseline in the Signs of Atopic Dermatitis score at Day 15, Day 29, and Day 57,
- The change from Baseline in the percent of body surface area (BSA) affected by AD at Day 15, Day 29, and Day 57,
- The proportion of subjects with IGA success defined as an IGA score of "Clear" (0) or "Almost Clear" (1) with at least a 2-grade improvement from Baseline at Day 15, Day 29, and Day 57,
- The absolute and percent change from Baseline in the Eczema Area Severity Index (EASI) score at Day 15, Day 29, Day 57, and Day 85,

- Change from Baseline in the subject's reports of pruritus obtained daily on a Patient Diary,
- Time to improvement of pruritus (change of ≥ 4 in the Worst Itch Numerical Rating Score [WI-NRS, 0 – 10 score]),
- Subject's assessment of the change in their AD from Baseline to Day 85 (Patient Reported Outcome [PRO]), and
- The change from Baseline to Day 29, and Day 57, and Day 85 in the Signs of AD score for the target lesion (selected sites).

Safety outcome measures to be assessed are:

- Reported adverse events (AEs) including treatment-emergent (TEAE) monitored from time of consent through the end of study,
- Changes in clinical labs including complete blood count (CBC), chemistry, and urinalysis between Baseline and Day 85, and
- Subject's reports of burning/stinging obtained during visits on Day 1, Day 15, Day 29, Day 57, and Day 85.

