4.3. Reasons for Withdrawal or Termination

If a subject is withdrawn from the study, the subject's enrollment in the study will terminate and study drug application will be discontinued. Efforts will be made to perform all assessments scheduled for the Day 85 Visit prior to subject withdrawal. Subjects may be replaced after consultation with the sponsor.

A subject may be withdrawn from further study participation under the following circumstances:

- At the subject's request.
- Noncompliance with protocol by the subject as determined by the study site staff and investigator.
- Adverse Event (decision to be removed from study made by either the investigator or subject). The investigator must notify the sponsor immediately if a subject is withdrawn because of an AE.

- Decision by the investigator or sponsor that termination is in the subject's best medical interest or administrative decision for a reason other than that of an AE.
- Lost to follow-up, as determined by failure to respond to at least 2 telephone calls followed by certified letter sent to the subject's last known address. All attempts to contact the subject must be documented in the subject's source documents.
- Sponsor decision to halt the entire study.

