6.3.9. Schedule of Events Table

The Schedule of Events is provided in Table 4.

Table 4 Time and Events Schedule

Parameter	Screening Visit ^a (-28 to Day 1)	Baseline Visit (Day 1)	Day 15 Visit (Day 15 ±3 day)	Day 29 Visit (Day 29 ±3 days)	Day 57 Visit (Day 57 ±5 days)	Day 85 Visit ^b (Day 85 ±5 days)
	Visit 1	Visit 2	Visit 3	Visit 4	Visit 5	Visit 6
Written informed consent/assent	X					
Medical history/ Review of systems	X	X ^a				
Demographics	X					
Height and weight measurement	X					
Urine pregnancy test (WOCBP only)	X	X ^a		X	X	X
Urine drug screen	X	X ^a				
Eligibility criteria review	X	X ^a				
IGA	X	X ^a	X	X	X	X
Body Surface Area (BSA) of AD	X	X ^a	X	X	X	X
Signs of AD score		X	X	X	X	X
EASI score		X	X	X	X	X
Pruritus Score (I-NRS)		X	X	X	X	X
Laboratory blood draw (CBC and chemistry)		X				X
Urine collection for urinalysis		X				X
Photographs and Signs of AD scoring of target lesion (selected sites)		X	X	X	X	X
Randomize subject		X				
Study drug administration in clinic		X	X	X	X	
Study drug administration at home		Day 1 pm to Day 84 pm; final application prior to Day 85 Visit				
Concomitant medications query	X	X ^a	X	X	X	X
Adverse experience query		X	X	X	X	X
Weigh and Dispense study drug		X		X	X	
Collect and Weigh study drug			X ^c	X	X	X
Dispense Diary		X		X	X	
Collect Diary and review compliance			X ^c	X	X	X

^a If subject meets eligibility criteria, Screening and Baseline Visit can occur on the same day. If Screening and Baseline Visit are not concurrent, review of eligibility, Review of Systems, UPT, UDS, BSA of AD, IGA, and concomitant medications query will be repeated at the Baseline Visit.

^b If subject discontinues treatment early, Day 85 evaluations will be performed when possible.

^c On Day 15, review compliance only.

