### 6.1.3 Visit Windowing

Data will be summarized based on nominal visit indications with the exception of data captured at early termination and unscheduled visits. Data from early termination and unscheduled visits will be summarized based on mapped visit values. The analysis windows for early termination and unscheduled visits are presented in the following table.

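### Protocol 6.3.8 leaves adverse-event leavers out of the request for exit assessments, and exit laboratory results recorded at an early-termination visit before Day 71 reach no planned laboratory table

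*Protocol*

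**What the plan says.** **Exit assessments.** Four places in the protocol deal with subjects who leave early.

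- Section 6.3.8: "If a subject terminates the study early for reasons other than an AE, attempts will be made to complete the assessments" of the Day 85 Visit.
- Protocol Summary, Methods: "If a subject discontinues from the study early, all Day 85 assessments will be completed".
- Section 4.3: "Efforts will be made to perform all assessments scheduled for the Day 85 Visit prior to subject withdrawal". The same section names as a withdrawal reason "Adverse Event (decision to be removed from study made by either the investigator or subject").
- Table 4, note b: "If subject discontinues treatment early, Day 85 evaluations will be performed when possible".

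**Laboratory tests.** Under Protocol 6.2.1, "a CBC, chemistry, and urinalysis will be conducted at the Baseline and Day 85 Visits", so there is one scheduled post-Baseline sample. The safety endpoint in Protocol 3.2 is "Changes in clinical labs including complete blood count (CBC), chemistry, and urinalysis between Baseline and Day 85".

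**Analysis.** SAP 6.1.3 states: "Data will be summarized based on nominal visit indications with the exception of data captured at early termination and unscheduled visits". Those exceptions are placed by study day, in windows that apply to efficacy and safety data alike. Early-termination data before Day 9 are not analysed. Data whose mapped visit has no planned analysis are also left out. SAP 6.11.4 plans laboratory summaries at Baseline and Day 85 and shifts between the two, and the table shells match. SAP 6.1.5 imputes nothing outside efficacy. All visits remain in the listings.

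**The concern.** Safety is a named objective. A maximal dose of 7 mL twice daily at 30 mg/mL is 7 x 2 x 30 = 420 mg of cannabidiol a day for 84 days, against 180 mg a day for 28 days in the earlier atopic dermatitis study (Protocol 1.2.3). With one scheduled post-Baseline sample, an early leaver's exit sample is the only scheduled laboratory result on treatment.

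Section 6.3.8 carries the heading a site would look for, and it omits the leavers whose exit safety data matter most. A missing exit IGA matters less, because IGA from earlier visits is kept and carried forward. The exception is a subject who leaves before any post-Baseline efficacy assessment: SAP 6.4.2 then drops that subject from the ITT population.

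The second part is separate. Even where an early leaver attends and is sampled, the result may enter no tabulated comparison between the arms, so the laboratory tables would describe mainly subjects who reach Day 71 or later.

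**Working it through.** The plan gives no figure to reproduce here. The check is a comparison of texts and then a day-by-day application of the SAP windows.

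**Step 1. The four early-exit instructions side by side.**

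| Place | Who is covered | Strength of the request |
|---|---|---|
| Summary, Methods | anyone who discontinues early | to be completed |
| 4.3 | any withdrawn subject, adverse event included | efforts |
| Table 4, note b | anyone who stops treatment early | if possible |
| 6.3.8 | non-AE leavers only | attempts |

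The first three differ in strength, but none exempts AE leavers. Section 6.3.8 alone does.

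**Step 2. Where an early-termination laboratory result goes (SAP 6.1.3 with 6.11.4).**

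| Study day | Mapped visit | In a laboratory table? |
|---|---|---|
| before 9 | none | no |
| 9 to 21 | Day 15 | no, no laboratory analysis planned |
| 22 to 42 | Day 29 | no, as above |
| 43 to 70 | Day 57 | no, as above |
| 71 to 98 | Day 85 | yes |

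The tables concerned are four summaries (14.3.2.1.1, 14.3.2.2.1, 14.3.2.3.1, 14.3.2.3.3) and three shift tables (14.3.2.1.2, 14.3.2.2.2, 14.3.2.3.2): 4 + 3 = 7.

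**Step 3. Share of possible exit days.** Days 2 to 84 are 83 days. Days 2 to 8 are 7, Days 9 to 70 are 62 and Days 71 to 84 are 14. (7 + 62) / 83 = 69 / 83 = 83%. This counts days, not subjects.

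**Step 4. Illustration per 100 subjects per arm.** The documents give no dropout rate, exit timing, sampling share or AE share, so all of these are assumed. Dropout is taken as 10% to 20%.

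- Exits uniform over Days 2 to 84, all sampled and recorded at an early-termination visit: 10 x 0.831 = 8.3 to 20 x 0.831 = 16.6 with a result outside the tables.
- The same with half sampled: 4.2 to 8.3.
- Half of exits on Days 71 to 84, all sampled: 5 to 10. No exits on those days, all sampled: 10 to 20.
- Exits entered under the nominal Day 85 visit: 0.
- AE leavers, at an assumed 20% to 40% of exits: 10 x 0.2 = 2 to 20 x 0.4 = 8. Those who miss exit assessments because of 6.3.8 range from 0, if sites follow the other three places, to 2 to 8, if all follow 6.3.8.

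**The case against.** **On 6.3.8.** Section 6.3.8 does not forbid assessing AE leavers, and three other places, including the schedule of events, ask for it. Other instructions also cover these subjects: Protocol 7.3 and 7.4.2 require adverse events to be followed until they resolve or stabilise, and 12.1.1 asks for thorough documentation of the outcome when a treatment-limiting event causes withdrawal. All of this is right and lowers the risk. None of it requires an exit laboratory sample, so the conflict stands.

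**On the laboratory tables.** The SAP implements the protocol: the endpoint in 3.2 and the shift tables in 9.3.2 both run from Baseline to Day 85. Keeping a sample taken after a few days of exposure out of a 12-week shift table is defensible. That stands, and it makes this part an improvement to a design choice. Protocol 9.3.2 also says abnormal findings will be summarised as well as listed, without naming a time point. This supports the addition but does not demand it.

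**On visibility.** A reader might infer that early leavers' results are lost, or that the arms can be compared only through events reported as AEs. The documents do not support this. The laboratory listings are headed by treatment group and show each result with its reference range and clinical significance. SAP 6.11.4 adds a listing of abnormal findings, and an abnormality reported as an AE reaches the TEAE tables. What is missing is a tabulated summary by arm.

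**On recording.** Table 4 has no early-termination column and hangs note b on the Day 85 Visit, so sites may enter exits there, and SAP 6.1.3 would then keep them. The SAP and 6.3.8 both name early-termination visits as distinct, so the other reading is natural. The documents do not settle it.

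**Conclusion.** Both parts hold, and the point is minor. Protocol 6.3.8 conflicts with three other places, and a site that follows it alone could leave an AE leaver without any scheduled post-Baseline laboratory result. The Day 71 cut-off is exact for results recorded at an early-termination visit, which enter none of the 7 laboratory tables if taken earlier.

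The number of subjects affected is unknown and may be 0 for either part. The figures per 100 rest wholly on assumed dropout, timing, sampling and AE share, and 83% must not be read as a share of leavers. The direction of any effect on the laboratory tables is also unknown. A reader might go further and call the SAP wrong or the primary result unsafe. Neither follows: the SAP matches the protocol endpoint, the primary analysis method is untouched, the tests are declared exploratory, and the medical monitor reviews safety data throughout.

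**What to change.** The two changes are independent.

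1. **Protocol 6.3.8.** At the next amendment, delete the words that confine the request to non-AE reasons, so that the section agrees with the Summary, 4.3 and Table 4 note b. This adds no procedure. An amendment needs sponsor and IRB/EC approval (Protocol 11.1.2), so it need not be raised for this alone.
2. **SAP 6.11.4.** Keep Day 85 as the main display. Add a supplementary summary and shift on the last observed post-Baseline laboratory value from any scheduled, unscheduled or early-termination visit. Exempt it from two exclusions in 6.1.3: data before Day 9, and data mapped to a visit with no planned analysis. The rule on data after Day 98 can stay.

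The SAP change takes about two sentences of text plus shell work, programmed once per shell and repeated. It covers 28 blood analytes: 14 in the SAP CBC shell, which lists ANC and neutrophils separately, and 14 chemistry tests in Protocol 6.2.1. Urinalysis comes on top. It needs no new data collection. Its drawback is that it pools different lengths of exposure, so it supplements the Day 85 tables and should not replace them.
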